### **IV) Method Monitoring:**

**A] Data Monitoring:** An independent Data Monitoring Committee (DMC) will monitor the results of the study. The Committee will include the trial's supervisors, who will periodically review the trial data and identify the need for any adjustments or modifications during the study.

**B] Interim Analysis:** no interim analysis will be performed during the study.

**C] Harm:** The main operator will document and report any harms or unwanted effects during the study intervention to the trial supervisors. Also any unpleasant experience will be reported by the patient in the final questionnaire at the end of the retraction. The main operator will be responsible for the management of any adverse effects or unfavorable side effects resulting from the appliance.

**D] Auditing:** The supervisor will follow up and review the different interventions and resulting data. And he will periodically follow up the trial progress including recruitment of patients, allocation of participants to study groups; adherence to interventions and reporting of harms. A meeting with the senior supervisor will be set every 3 months to monitor the progress of the study and the need for any adjustments.

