## **Secondary objective:**

Evaluating the rate of “En-masse retraction” using frictionless Versus friction mechanics, root resorption, pain and discomfort during retraction. In addition to this, changes in vertical position (extrusion/ intrusion), tip and torque of anterior teeth will be measured following “En-masse retraction” using frictionless versus friction mechanics.

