## C] Interventions:

➤ **Medical History Questionnaire:**

For every patient, to exclude the presence of any systemic condition interfering with orthodontic treatment.

➤ **Clinical Examination:**

Oral structures will be examined to identify caries, fracture or missing teeth. Gingival tissues will be carefully examined for any gingivitis, periodontitis, recession, or lesions.

> **Diagnosis**

Check the potential patient to fulfill the previously mentioned inclusion criteria. Every participant will be asked to sign an informed consent about the study. Full set of records (study models, panorama radiograph and lateral cephalometric radiographs, photos) will be taken for every patient as part of the routine procedure for treatment of patients in the clinic of the Orthodontics and Dentofacial Orthopedics Department, Future University in Egypt.

> **Clinical Procedure:**

After taking pre-treatment records, every patient will receive:

- Bonding of all teeth except for first premolars and banding/bonding the first and second molars will be done using Roth prescription brackets (0.022 x 0.028 slot)\*.
- Miniscrews will then be placed in the upper arch between the second premolar and first molar\*\*.
- The patient will be referred for extraction of first premolars.
- Anchorage will be secured, followed by Leveling and alignment for the bonded and banded teeth through following the wire sequence: 0.014 Nitti, 0.016×0.022 Nitti and 0.017×0.025 StSt.

- After levelling and aligning is completed (right before retraction), the patient will be referred for the uptake of pre-intervention records:
  - a- CBCT
  - b- Impression and models
  - c- photo (Extraoral & Intraoral)
  - d- pain questionnaire

➢ **Acquisition of pre-intervention records:**

- The patient will be referred for the uptake of a CBCT, which are considered to be the T0 records.
- Impressions will be taken before retraction (without the archwire in place) followed by digital scanning of produced models.
- Photos (Extraoral & Intraoral)
- Pain questionnaire distributed with explanatory session on it

➢ **Beginning of Retraction:**

*Frictionless group:*

- A braided ligature wire extended between the second premolars and miniscrews will be used for proper indirect anchorage control.
- Closing retraction T-loops will be fabricated using 0.017 x 0.025 TMA wire. The loop will be positioned halfway the extraction space and the canine. [40,41].
- A gable angle of 45° will be added to the posterior segment.

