***Friction group:***

- Crimpable hooks added to the arch wire (0.017"x0.025" Stainless steel) distal to the lateral incisor passing near the center of resistance of the anterior segment.
- A ligature wire extending between the second premolar and miniscrews will be used for proper anchorage control.
- Retraction will start on a 0.017"x0.025" Stainless steel wire using elastomeric chain (force applied will be 200 g per side) [43] extending between the crimpable hooks and the miniscrews.
- The force will be measured by a force gauge and reactivated every 4 weeks maintaining constant force of retraction all over the retraction phase.

➢ **Follow up visits**

Patients will be asked to attend for follow up sessions every 4 weeks for:

- Evaluation miniscrews stability.
- Replacement of the power chain to maintain a force of 200 gm per side.
- Reactivation of the T-loop by further distal activation and cinch back.
- Impression taking to determine the anchorage loss

➤ **Criteria for discontinuing or modifying the allocated intervention:**

In cases of prolonged swelling or pain related to the miniscrews, the patient will be given strict oral hygiene measures and may wait for three weeks before the beginning of retraction.

In cases of loose or broken miniscrews, the screw will be removed and replace the miniscrew after total resolution of the inflammation.

➤ **Criteria for Ending the retraction:**

a-class I canines

b-normal overjet

c- closure of extraction space

d- reaching good profile

Ø **Post-retraction Questionnaire:**

The patients of both groups will be asked to fill in questionnaires regarding their experience with their allocated technique during the whole retraction period from day of extraction till the end of retraction.

Ø **Retraction records**

Following “En-masse retraction”, patients will be referred to the same radiology center to acquire the final cone-beam CT to assess the movement and inclination of anterior teeth.

The final dental model will be used to assess the rate of retraction and molar anchorage loss achieved throughout the study.

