## D] Outcomes

[figure not shown]
**Primary outcome:** is to monitor the anchorage loss during “En-masse retraction”. All outcomes will be assessed as the difference between T0 at the start of retraction and T1 after complete space closure.

**Secondary outcomes:** is to monitor the changes in the anterior teeth position (final anterior teeth tip, torque and vertical position), rate of space closure, presence of any root resorption and pain associated with the different methods used for retraction.

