## **E] Participant timeline:**

1. The principle investigator will screen the potential patients through careful clinical examination of patients at the Orthodontics and Dentofacial Orthopedics department, Faculty of Oral and Dental Medicine, Future University in Egypt.
2. All recruited patients should fulfill the previously mentioned inclusion and exclusion criteria.
3. Every participant will be asked to sign an informed consent before the beginning of the study.
4. Pre-intervention records will be taken for each participant after enrollment to ensure proper diagnosis.
5. The principle investigator will randomly allocate the patients to one of the intervention groups.
6. Anchorage will be secured by placement of miniscrew, followed by extraction of the first premolar.
7. Active intervention will begin after proper levelling and alignment of teeth through following the wire sequence: 0.014 NiTi, 0.016×0.022 NiTi and 0.017×0.025 StSt.
8. The principle investigator will take pre-retraction records for every participant T0.
9. In Friction mechanics group, Power chain is used for anterior segment retraction while in Frictionless group, T-loop is used for retraction.
10. Each patient will come every 4 weeks for follow up visit, for appliance activation and uptake of impression for interim records.
11. After complete space closure, the principle investigator will take post-retraction records for each participant T1.

- 12.Every patient will fill up a questionnaire regarding his experience during treatment.
- 13.The principle investigator will continue the normal treatment and achieve proper finishing for every patient after the end of the study.

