## **F] Sample size calculation:**

Our sample size calculation is based on a previous study comparing the effect of friction and frictionless mechanics. Using PS software output, we are planning a study of a continuous response variable from independent Group I and Group II subjects with 1 Group I(s) per Group II subject. In a previous study the response within each subject group was normally distributed with standard deviation 0.76. If the true difference in the Group II and Group I means is 1.0, we will need to study 10 Group II subjects and 10 Group I subjects to be able to reject the null hypothesis that the population means of the Group II and Group I are equal with probability (power) 0.8. The Type I error probability associated with this test of this null hypothesis is 0.05. Considering drop out a sample size 15 per group is appropriate.

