##### ***Secondary outcomes:***

**1. Retraction rate:** to assess the antero-posterior movement of anterior teeth and first molars, the principle investigator will take study models for every participant monthly during the follow up visits. Then will digitize the models and identify the landmarks, reference lines and planes on the pre, interim and post-retraction digital dental models for measurements reading. Also, by identifying the landmarks, reference lines and planes using CBCT taken before and after the completion of retraction.

**2. Pain:** each patient will fill a questionnaire regarding his treatment experience in a Visual Analog Scale (VAS) scoring from 1-10 by making a handwritten mark on a 10-cm line that represents a continuum between “no pain” on the left end (0 cm) of the scale and the “worst pain” on the right end of the scale (10 cm). The questionnaire will include several questions related to oral hygiene, pain and discomfort experienced throughout the trial.

**3. Root resorption:** will be accessed by the principle investigator via CBCT taken before and after the completion of retraction. The resorption will be identified using

scoring system of Levander and Malmgren that classifies it into 5 grades: 0, no root resorption; 1, mild resorption, with the root of normal length and only an irregular contour; 2, moderate resorption, with small areas of root loss and the apex having an almost straight contour; 3, severe resorption, with loss of almost one third of root length; and 4, extreme resorption, with loss of more than one third of the root length.

**4. *Anterior teeth torque:*** will be accessed by the principle investigator via CBCT taken before and after the completion of retraction. The principal investigator will identify the landmarks, reference lines and planes, then will interpret the measurements in degrees.

**5. *Anterior teeth extrusion/intrusion:*** will be accessed by the principle investigator via CBCT taken before and after the completion of retraction. The principal investigator will identify the landmarks, reference lines and planes, then will interpret the measurements in millimeters.

**6. *Anterior teeth tip:*** will be accessed by the principle investigator via scanned digital models taken before and after the completion of retraction.

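### Pain during retraction rests on one retrospective form whose window starts at extraction, with no patient report at the four-weekly visits or on early stopping

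*Protocol*

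**What the plan says.** - **Objective.** The protocol's Secondary objective lists "root resorption, pain and discomfort during retraction".
- **T0.** Under C] Interventions, the records taken after levelling and just before retraction include a pain questionnaire: "Pain questionnaire distributed with explanatory session on it".
- **After retraction.** The Post-retraction Questionnaire paragraph in the same section asks about experience with the allocated technique "during the whole retraction period from day of extraction till the end of retraction". E] Participant timeline puts this form at step 12, after the T1 records of step 11.
- **Visits in between.** Step 10 of the timeline reads "Each patient will come every 4 weeks for follow up visit, for appliance activation and uptake of impression for interim records". The Follow up visits list adds miniscrew stability. Neither list names pain or unwanted effects.
- **Scoring rule.** D] Outcomes states: "All outcomes will be assessed as the difference between T0 at the start of retraction and T1 after complete space closure".
- **Harms.** IV) Method Monitoring, C] Harm has the main operator document harms while the intervention runs, and then adds: "Also any unpleasant experience will be reported by the patient in the final questionnaire at the end of the retraction".
- **Scale.** III) A] Secondary outcomes, 2. Pain, describes a questionnaire answered "in a Visual Analog Scale (VAS) scoring from 1-10 by making a handwritten mark on a 10-cm line", with the painless end of the line at 0 cm. The Outcome measure table also gives 1-10.

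**The concern.** The objective concerns pain produced by two retraction techniques. The planned measurement is a single look back, taken when retraction is over, across a period that begins well before the techniques differ. Part of what patients recall will be pain from extraction and from levelling, neither of which is under comparison. The T0 score falls inside that same period, so subtracting it does not isolate retraction.

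A patient who leaves before the end has no scheduled occasion to report pain or unwanted effects in their own words. The Rationale notes that loops may be uncomfortable for some patients, so such losses could be related to the outcome. What is at stake is whether the pain comparison answers its own question, and whether patient-reported tolerability covers everyone randomised. These are collection times, so no later analysis plan can recover scores that were never taken.

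**Working it through.** **1. Order of events** (C] Interventions; E] Participant timeline; II) C] Implementation)

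| Step | Event | Do the arms differ? | Inside the final form's window? | Pain score stated? |
|---|---|---|---|---|
| 5 | Allocation, before levelling | no | no | no |
| 6 | Miniscrews, then extraction | no | yes, from extraction | no |
| 7 | Levelling and alignment | no | yes | no |
| 8 | T0 records | no | yes | questionnaire handed out |
| 9-10 | Retraction, visits every 4 weeks | **yes** | yes | **no** |
| 11 | T1 records | – | end of window | no |
| 12 | Final questionnaire | – | – | one retrospective form |

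The only phase in which the arms differ has no stated pain score of its own. The protocol gives no length for retraction. Whatever the length, the number of scheduled in-treatment scores is zero.

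**2. What the T1-minus-T0 difference contains**

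Let F be the recalled score on the final form, R the patient's pain in retraction, E the pain of extraction and levelling, and w the weight the patient gives to retraction when making one mark:

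F = w·R + (1 − w)·E, with 0 ≤ w ≤ 1.

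Treatment is the same in both arms until retraction starts, so randomisation gives E and the T0 score B the same expectation in each arm. The expected difference between arms in F − B is then

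w·(mean R, frictionless − mean R, friction).

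Two things follow. First, the arm difference shrinks by the factor w. The protocol gives nothing from which to estimate w; it equals 1 only if patients ignore everything before retraction, which is not what the form asks. Second, B describes a time already inside F's window. The difference is therefore not a change from before the window to after it, and it does not remove E.

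**3. Early leavers**

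Inputs from F] Sample size calculation: SD 0.76, difference 1.0, power 0.8, type I error 0.05, 10 per group, then "Considering drop out a sample size 15 per group is appropriate".

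The plan's own figure reproduces for the primary outcome:
- Normal approximation, two-sided: 2 × (1.960 + 0.842)² × 0.76² / 1.0² = 2 × 7.85 × 0.5776 = 9.07, rounded up to 10 per group.
- Two-sample t-test: 10.12 per group; power at 10 is 0.795.

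Margin: 15 − 10 = 5 per group, and 5/15 = 33%. No dropout rate or reason is stated. Up to a third of an arm could leave within the plan's tolerance, each without the only post-baseline pain form. For them, C] Harm leaves the operator's record. D] Blinding says that the operator cannot be blinded, and such a record yields no pain score.

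**4. Scale**

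The line runs from 0 to 10 cm and the score from 1 to 10. Marks from 0 to just under 1 cm, which is 1/10 = 10% of the line and includes its painless end, have no valid score.

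**The case against.** **Harms in early leavers are not lost altogether.** A reader might infer that a patient who stops because of harm never has it reported. The protocol does not support that. The sentence just before the one on the final questionnaire has the operator document and report harms during the intervention, D] Auditing has the supervisor follow harm reporting, and miniscrews are checked at every visit. What stands is narrower: these patients have no form of their own, and the record comes from someone who knows the allocation.

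**The final form is retrospective.** A reader might also argue that pain is read at T0 and T1, when no retraction force acts, so that the score contains no retraction pain. The Post-retraction Questionnaire paragraph and the Pain item both ask about experience over a period, which makes that reading unlikely. The fault is the window and the single recall.

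**The schedule is partly inferred.** The Outcome measure table mentions pain scoring sheets without timing, and the T0 questionnaire is said to be handed out, not completed. Sheets kept through retraction would be compatible with this. No section says so, however, and the stated completion step is at the end. If a diary was intended, the protocol needs to state it.

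**A single global rating is defensible** as a measure of overall experience. That is fair, but the stated objective is pain during retraction, and the form's window does not match it.

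**Size and direction are not established.** The 33% is the whole enrolment margin for all causes. Nothing shows that losses would be harm-related or would differ by arm, so it cannot be said that the less tolerable technique would look better.

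**Conclusion.** The point holds in this limited form. As written, the pain comparison mixes retraction pain with extraction and levelling pain, applies a T1-minus-T0 rule whose T0 lies inside the recall window, and has no score from patients who stop early. The expected effect is dilution of any arm difference by an unknown factor w, together with possible selection from missing forms, whose ceiling under the plan's own margin is 5 of 15 per arm. The 1-10 score contradicts the 0 cm anchor on the face of the text.

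This rests on three assumptions: that the questionnaire listed with the T0 records is filled in then, that the pain sheets have no further schedule, and that pain falls under the rule for all outcomes. Pain is a secondary outcome, so the primary comparison is untouched. The change should be made, because the protocol cannot otherwise meet this objective.

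**What to change.** 1. **Visits.** In the Follow up visits list and timeline step 10, add that at each four-weekly visit, before reactivation, the patient marks the 10-cm line and answers one open question on unwanted effects, both for the time since the last activation.
2. **T0.** State that the T0 questionnaire is completed at T0, not only handed out.
3. **Comparison.** Compare the arms on each patient's mean visit score, adjusted for the T0 score. In D] Outcomes, exempt pain from the T1-minus-T0 rule.
4. **Early stopping.** A patient who stops early completes the final questionnaire at the last attended visit. If a patient leaves without notice, the visit scores already collected remain usable.
5. **Scale.** Score the line 0-10 in the Outcome measure table and in the Pain item.

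The visits already take place, so the cost is a short form and a little more data entry. Two limits remain: recall of about four weeks at each visit, and a number of visit scores that differs between patients because retraction ends at different times. Both should be acknowledged in the protocol.

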## **V) Ethics and dissemination:**

### **A] Research Ethics Approval:**

The Ethical committee in Future University in Egypt will review the protocol before they approve it. The research Ethics committee will evaluate the different interventions of the study to ensure its ethical validity and the potential benefits to the participants.

### **B] Protocol amendments:**

The main investigator will be responsible to complete a formal amendment in case of any modifications or adjustments to protocol that may affect the conduct of the study, as changes in the study design or intervention procedures. The Orthodontics and Dentofacial Orthopedics department, Faculty of Oral and Dental Medicine,

Future University in Egypt and the Ethics Committee will approve such amendment before proceeding in the study.

**C] Consent:**

The main investigator will be in charge for detailed explanation and elaboration of the different steps of the study interventions for each patient. Then will ask every participant to sign a written consent before they begin treatment. The consent will be written in Arabic.

**D] Confidentiality:**

The main investigator will store any personal information about the participants collected during the study separately from study records in locked files in areas with only access to the supervisors responsible for auditing and analysis. Also, will keep the files in the Department Of Orthodontics and Dentofacial Orthopedics, Faculty of Oral and Dental Medicine, Future University in Egypt and will identify all the reports, data and administrative forms by a coded ID number to maintain participant confidentiality. Participant information won't be used outside the study except with written permission of the participant.

**E] Declaration of interests:**

No financial interests are to be declared by the supervisors and the principle operator. This study is a part of a Masters' degree in Orthodontics and Dentofacial Orthopedics department, Faculty of Oral and Dental Medicine, Future University in Egypt and it is self-funded by the principal investigator.

**F] Access to data:**

The supervisors and the principal investigator will only have access to the data of the study. All the data will be secured by a password to maintain confidentiality. No other parties are allowed to assess the results until the study is terminated and the conclusions are revealed.

**G] Ancillary and post-trial care:**

Any complication associated with the intervention will be managed by the principal operator. Then the two group of patients will continue their regular orthodontic treatment according to the treatment plan described for each case.

**H] Dissemination Policy:**

The trial results will be available to the participants, health care professionals and the public by publication of the study in high quality national and international journals. The principal investigator will present a copy of the thesis at the Faculty of Oral and Dental Medicine, Future University in Egypt library and will distribute additional copies among the main universities in Egypt.

